### 6.16.1 Adhesion

Amendment 4: Version 5.0 May-08-2013  
Amendment 3: Version 4.0 December-11-2012  
Amendment 2: Version 3.0 October-31-2012  
Amendment 1: Version 2.0 August-02-2012  
Final Protocol May-25-2012

Adhesion will be evaluated by site personnel on Visit 6 (Day 42) and Visit 7 (Day 49). The 9-hr assessment will be performed immediately prior to patch removal. Findings will be recorded as an estimate of the percentage of the system surface in contact with the skin, according to the scale presented in Table 1.

*The system should not be secured with adhesive tape or occlusive dressing of any type.* In the unlikely event that a patch should detach completely, the same patch should not be reapplied and a new patch must not be applied. The time and activity at the time of detachment must be documented.

**Table 1:** Adhesion

Score	Definition
0	$\geq 90\%$ adhered (essentially no lift off the skin)
1	$\geq 75\%$ to $< 90\%$ adhered (some edges only lifting off the skin)
2	$\geq 50\%$ to $< 75\%$ adhered (less than half of the patch lifting off the skin)
3	$>0\%$ to $< 50\%$ adhered but not detached (more than half of the patch lifting off the skin without falling off)
4	0% adhered – Patch detached (patch completely off the skin)

Additionally, every day at home, prior to patch removal, adhesion will be evaluated by the subject or parent/caregiver. Adhesion will be evaluated according to a Yes/No question. If patch is detached then subject/parent/caregiver will be asked to make a note of the time of detachment and will be asked not reapply the detached patch or apply a new patch. Subject/parent/caregiver will be required to answer the following questions:

1. Is the patch fully attached to the skin? Yes/No
2. If 'No', did the patch fall off completely? Yes/No
  - a. If 'Yes', then enter time of patch detachment (hh:mm) and activity at the time of detachment.

### **6.16.2 Discomfort**

While assessing discomfort, the evaluator must ask the subject, "Are you experiencing any discomfort related to the patch?" If the answer is "no", the overall level of discomfort will be rated as zero. If the answer is "yes", the evaluator will ask the subject to rate the discomfort as mild, moderate, or severe. If the discomfort is mild, moderate, or severe, the evaluator will probe the subject further, i.e. "Describe your discomfort". The type of discomfort should be specified

Amendment 4: Version 5.0 May-08-2013

Amendment 3: Version 4.0 December-11-2012

Amendment 2: Version 3.0 October-31-2012

Amendment 1: Version 2.0 August-02-2012

Final Protocol May-25-2012

and recorded i.e., itching, burning, or other. Any discomfort will be followed to resolution. Discomfort should be recorded and rated according to the scale in Table 2.

**Table 2:** Experience of Discomfort

Score	Definition
0	No discomfort
1	Mild discomfort
2	Moderate but tolerable discomfort
3	Severe, intolerable discomfort
4	Patch not present

For discomfort scores greater than 0, discomfort will also be evaluated after d-ATS patch application on Day 35, Day 42, and Day 49 using the 10-point Wong-Baker Faces or Visual Analog Scale (age dependent). A  $\pm$  15 minute window is permissible.

Additionally, every day at home, prior to patch removal, discomfort will be evaluated by the subject/parent/caregiver. Discomfort will be evaluated according to a Yes/No question. Subject will be required to answer the following questions:

1. Are you experiencing any discomfort? Yes/No
2. If 'Yes', then describe your discomfort? Burning, itching or other

***NOTE: Signs and/or symptoms of discomfort related to the patch should NOT be recorded as AEs, unless they occur at a site different from the application site or if the subject or patch application site is discontinued prematurely from the study due to discomfort at the patch site or the symptoms of discomfort are so severe that in the investigator's judgment it should be recorded as an AE. If discomfort is recorded as an AE then the AE will be followed to resolution or up to 30 days following patch removal, whichever comes first.***

#### **6.16.3 Irritation**

The application site will be graded according to the following grading scales. Half grades will not be assigned if reactions fall between the unit grades, rather the more severe of the two grades will be assigned. The examination and readings will be performed by trained evaluators only, except for the home evaluations by parent/caregiver. Findings will be graded and recorded according to the following two scales presented in Table 3 and Table 4.

Amendment 4: Version 5.0 May-08-2013

Amendment 3: Version 4.0 December-11-2012

Amendment 2: Version 3.0 October-31-2012

Amendment 1: Version 2.0 August-02-2012

Final Protocol May-25-2012

**Table 3:** Dermal Response Scale

Score	Skin Appearance
0	No evidence of irritation
1	Minimal erythema, barely perceptible
2	Definite erythema, readily visible; or minimal edema; or minimal papular response
3	Erythema and papules
4	Definite edema
5	Erythema, edema, and papules
6	Vesicular eruption
7	Strong reaction spreading beyond test (i.e., application) site

**Table 4:** Other Effects

Score (Numeric equivalent)	Observation
N (0)	No other effects
A (0)	Slightly glazed appearance
B (1)	Marked glazed appearance
C (2)	Glazing with peeling and cracking
F (3)	Glazing with fissures
G (3)	Film of dried serous exudates covering all or part of the patch site
H (3)	Small petechial erosions and/or scabs

Additionally, every day at home, prior to patch application and 30 minutes after patch removal, irritation will be evaluated by the subject/parent/caregiver by visually inspecting the patch application site. Irritation will be evaluated according to a Yes/No question. Subject will be required to answer the following questions:

1. Do you see any irritation? Yes/No
2. If 'Yes', then describe the irritation? Redness, swelling or other

Amendment 4: Version 5.0 May-08-2013  
 Amendment 3: Version 4.0 December-11-2012  
 Amendment 2: Version 3.0 October-31-2012  
 Amendment 1: Version 2.0 August-02-2012  
 Final Protocol May-25-2012

**NOTE: Signs and/or symptoms of skin irritation related to the patch should NOT be recorded as AEs, unless they occur at a site different from the application site or if the subject or patch application site is discontinued prematurely from the study due to irritation at the patch site and/or symptomatic intolerable irritation or the symptoms of irritation are so severe that in the investigator's judgment it should be recorded as an AE. If irritation is recorded as an AE then the AE will be followed to resolution or up to 30 days following patch removal, whichever comes first. In addition, a score of "N" (none) for the Other Effects Scale will be added as an option on the eCRF when no other effects are observed. This must also be noted on a source document.**

#### 6.16.4 Adhesive Residue

Immediately following the removal of the patch daily at home by subjects/parents/caregivers and on Visit 6 (Day 42) and Visit 7 (Day 49), the amount of adhesive remaining at the application site will be examined and graded according to the scale presented in Table 5.

If necessary, patch removal may be facilitated by gently applying an oil-based product (i.e., petroleum jelly, olive oil, or mineral oil) to the patch edges, gently working the oil underneath the patch edges. If any adhesive remains on the skin following patch removal, an oil-based product may be applied to patch sites in an effort to gently loosen and remove any residual adhesive that remains following patch removal. In the unlikely event that a patch remains tightly adhered despite these measures, the subject/parent/caregiver should contact the site personnel. Nonmedical adhesive removers and acetone-based products (i.e., nail polish remover) should not be used to remove patches or adhesive.

Table 5: Adhesive Residue

Score	Definition
0	None
1	Light
2	Medium
3	Heavy
4	Patch not present

#### 6.17 Adverse events

Per the International Conference of Harmonization (ICH), an adverse event is any untoward medical occurrence in a subject administered a pharmaceutical product that does not necessarily have a causal relationship with the treatment. An AE can therefore be any unfavorable and unintended sign, symptom, or disease temporally associated with the use of a medicinal product, whether or not considered related to the medicinal product. Pre-existing events, which increase in frequency or severity or change in nature during or as a consequence of use of a drug in

Amendment 4: Version 5.0 May-08-2013

Amendment 3: Version 4.0 December-11-2012

Amendment 2: Version 3.0 October-31-2012

Amendment 1: Version 2.0 August-02-2012

Final Protocol May-25-2012

clinical trials, will also be considered an AE. Adverse events may also include pre- or post-treatment complications that occur as a result of protocol-mandated procedures (e.g., invasive procedures such as biopsies).

Any medical condition or clinically significant laboratory abnormality with an onset date before the date of signing of Informed Consent is considered to be pre-existing, and should be documented as Medical History. Any new medical condition or clinically significant laboratory abnormality or an exacerbation of a pre existing condition with an onset date after signing of Informed Consent should be recorded as an AE.

Adverse events will be collected throughout the study beginning from the time the subject signs the consent form and up to 30 days following last patch removal. For all AEs the Investigator must pursue and obtain information adequate both to determine the outcome of the AE and to assess whether it meets the criteria for classification as a serious AE requiring immediate notification. Ongoing AEs, at the End of Study or Early Termination, will be followed until the event resolves or stabilizes at a level acceptable to the Investigator or up to 30 days after last patch removal, whichever occurs first. Follow-up beyond 30 days should be discussed with the medical monitor.

### ***6.17.1 Assessment of Adverse Events***

All clinical AEs occurring during the clinical study will be assessed by the Investigator and recorded including the date and time of onset and resolution, severity, relationship to study treatment, outcome and action taken with study treatment. The Investigator should attempt, if possible, to establish a diagnosis based on the presenting signs and symptoms. In such cases, the diagnosis should be documented as the AE and not the individual sign/symptom.

Severity of AEs will be graded on a three point scale: mild, moderate, severe.

- Mild discomfort noticed but no disruption of normal daily activity.
- Moderate discomfort sufficient to reduce or affect daily activity.
- Severe inability to work or perform normal daily activity

Relationship to study treatment should be assessed using the following definitions:

Amendment 4: Version 5.0 May-08-2013  
Amendment 3: Version 4.0 December-11-2012  
Amendment 2: Version 3.0 October-31-2012  
Amendment 1: Version 2.0 August-02-2012  
Final Protocol May-25-2012

**Probable (must have first three):** This category applies to those adverse events which are considered, with a high degree of certainty, to be related to the test drug. An adverse event may be considered probable, if:

- It follows a reasonable temporal sequence from administration of the drug.
- It cannot be reasonably explained by the known characteristics of the subject's clinical state, environmental or toxic factors, or other modes of therapy administered to the subject.
- It disappears or decreases on cessation or reduction in dose. (There are important exceptions when an adverse event does not disappear upon discontinuation of the drug, yet drug-relatedness clearly exists; e.g., (1) bone marrow depression, (2) tardive dyskinesias.)
- It follows a known pattern of response to the suspected drug.
- It reappears upon rechallenge.

**Possible (must have first two):** This category applies to those adverse events in which the connection with the test drug administration appears unlikely but cannot be ruled out with certainty. An adverse event may be considered possible if, or when:

- It follows a reasonable temporal sequence from administration of the drug.
- It may have been produced by the subject's clinical state, environmental or toxic factors, or other modes of therapy administered to the subject.
- It follows a known pattern of response to the suspected drug.

**Remote (must have first two):** In general, this category is applicable to an adverse event which meets the following criteria:

- It does not follow a reasonable temporal sequence from administration of the drug.
- It may readily have been produced by the subject's clinical state, environmental or toxic factors, or other modes of therapy administered to the subject.
- It does not follow a known pattern of response to the suspected drug.

Amendment 4: Version 5.0 May-08-2013

Amendment 3: Version 4.0 December-11-2012

Amendment 2: Version 3.0 October-31-2012

Amendment 1: Version 2.0 August-02-2012

Final Protocol May-25-2012

- It does not reappear or worsen when the drug is re-administered.

**Unrelated:** This category is applicable to those adverse events which are judged to be clearly and incontrovertibly due only to extraneous causes (disease, environment, etc.) and do not meet the criteria for drug relationship listed under remote, possible, or probable.

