**Double-Blind Treatment Period [Day 36 to Day 49; Visit 6 (Day 42) and Visit 7 (Day 49)]:**

Subjects who have reached an optimal dose will be randomized at Visit 5 to receive double-blind treatment. Administration of study medication will begin on Day 36 and continue up to Day 49 (end of Week 7). During Week 6 subjects will receive study patches in accordance with the randomization schedule and during Week 7 subjects will cross-over to receive the other study treatment per the randomization schedule. Subjects/parents/caregivers will be instructed to apply study patches to the hip once daily in the morning at approximately 8:00 am. Patches will be removed after 9 hours. Each day a new patch will be applied to the opposite hip. Subjects will be instructed to continue completing the daily dosing diary and the daily dermal diary. Subjects will return to the clinic for evaluations and analog classroom sessions in the laboratory classroom setting on Visit 6 (Day 42) and Visit 7 (Day 49). Site personnel will contact subjects by telephone on Day 39 and Day 46. All end of study procedures will be completed for subjects who are early discontinuations from the study.

**Follow-Up:** A safety follow-up by telephone 7- 10 days (Visit 8, Day 56 + 3 days) after last dose of study drug.

**Sample Size:** Sufficient number of subjects with ADHD will be screened to randomize approximately 90 subjects. Assuming a 20% dropout rate, it is expected that 74 subjects will complete the study. The Full Analysis Set population (FAS) will be used as the primary population for analysis of efficacy endpoints and is defined as subjects who have taken at least one dose of study medication.

Amendment 4: Version 5.0 May-08-2013

Amendment 3: Version 4.0 December-11-2012

Amendment 2: Version 3.0 October-31-2012

Amendment 1: Version 2.0 August-02-2012

Final Protocol May-25-2012

**Study Duration:** The duration of the study will be approximately 56 days for each individual subject (not including screening and washout).

**Study Population:** The study population will consist of children and adolescents 6 to 17 of age, who have been diagnosed with ADHD.

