### **6.19 Anticipated Adverse Events**

Some of the adverse events noted in more than one clinical trial of oral forms of d/l-amphetamine are: headache, decreased appetite, stomach ache, trouble sleeping, nervousness, mood swings, weight loss, dizziness, dry mouth, blurred vision, seizures (mainly in patients with a history of seizures), and slowing of growth in children. It should be assumed that the adverse event profile for the d-ATS should be similar to that found in clinical trials of oral d/l-amphetamine.

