Age will be calculated as (date of informed consent – date of birth + 1) / 365.25.

Baseline

Baseline is defined as data collected at Visit 0 (Day 0). If data was not collected at Visit 0, the last data available prior to Visit 0 will be used as the baseline data. However during the double

blind crossover phase change from baseline analyses will be performed taking the pre-dose data at the same classroom visit to be the baseline.

Body Mass Index

Body Mass Index (BMI) will be calculated as weight in kg / (screening height in m)².

Prior and Concomitant Medications

Prior medications are defined as those taken prior to the date of first dose of study medication. Concomitant medications are defined as those on or after the date of first dose of study medication through and including the day of the safety follow-up visit. Medications with a missing or incomplete start date will be assumed to be concomitant.

Concomitant medications will be assigned to either the Dose-Optimization Period or the double-blind Treatment Period of the study according to the start date, and will be summarized separately. Concomitant medications for which a missing or incomplete start date makes it impossible to determine which period of the study they started in will be counted as starting in the Dose-Optimization Period.

Treatment-emergent adverse event

A treatment-emergent adverse event (TEAE) is one which first occurs or worsens in severity after the first patch application and not later than 30 days following last patch removal. Adverse events are collected through the last study visit. Those AEs with a start date equal to the date of first patch application will be considered as TEAEs.

Adverse events for which a missing or incomplete start date makes it impossible to determine whether or not they were treatment-emergent will be counted as being treatment-emergent.

Adverse events will be assigned to either the Dose-Optimization Period or the double-blind Treatment Period of the study according to the start date, and will be summarized separately. Adverse events for which a missing or incomplete start date makes it impossible to determine which period of the study it started in will be counted as starting in the Dose-Optimization Period

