7.7.1 Adverse Events

Treatment-emergent adverse events will be assigned to either the open-label Dose-Optimization Period or the double-blind Treatment Period. TEAEs occurring in the safety follow up after the double blind Treatment Period will be reported under the double blind Treatment Period for the last treatment they received. TEAEs for which a missing or incomplete start and/or stop date makes it impossible to determine which period of the study they started in will be counted as starting in the Dose-Optimization Period. The subject's dose of study drug at the onset of the event will be determined for all TEAEs. If a missing or incomplete start date makes it impossible to determine the dose at onset, then the dose at onset will be set to the lowest dose in the study (i.e., 5 mg/ 4.76 cm²). Adverse events that start before the first patch application will be summarized separately. For summaries, TEAEs with missing severity are assumed to be severe, and TEAEs with missing relationship to study drug are assumed to be related.

Summary statistics for TEAEs will be presented separately for the SP population on all subjects combined during the Dose-Optimization Period and by treatment arm during the double-blind Treatment Period. All summaries of adverse events will consist of the number of events and the numbers and percentages of subjects who had the events being summarized.

All TEAEs will be classified by SOC and PT using the latest version of MedDRA dictionary. All TEAEs that occur after first patch application up to 30 days following last patch application will be summarized. Subjects may have more than one TEAE per SOC or PT. Unless otherwise specified, at each level of subject summarization in reporting the incidence of the AE, a subject will be counted once if the subject reported one or more events.

The following summaries will be presented separately for the Dose-Optimization Period and the double-blind Treatment Period by the dose being taken at the onset of the events and by MedDRA SOC, and preferred term:

- Overall summary of TEAEs
- TEAEs
- Treatment-related TEAEs
- TEAEs leading to premature discontinuation of study drug
- TEAEs by intensity.

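### AEs are assigned to study period by start date alone although onset time is recorded, so onsets before the first Day 36 patch count as double-blind; no Week 6/Week 7 cut is stated

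*Protocol*

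**What the plan says.** Protocol 6.17.1 has every clinical AE "recorded including the date and time of onset and resolution".

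SAP 5 does not use the time. It states: "Adverse events will be assigned to either the Dose-Optimization Period or the double-blind Treatment Period of the study according to the start date". For treatment emergence it adds: "Those AEs with a start date equal to the date of first patch application will be considered as TEAEs". SAP 7.4.1 sets the first double-blind dose at the day after Visit 5, which is also a calendar date.

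SAP 7.7.1 repeats the two-way split: "Treatment-emergent adverse events will be assigned to either the open-label Dose-Optimization Period or the double-blind Treatment Period". Double-blind AEs are then shown by treatment arm and by the dose being taken at onset. The subject's "dose of study drug at the onset of the event will be determined for all TEAEs", and a fallback dose applies under this condition: "If a missing or incomplete start date makes it impossible to determine the dose at onset". Follow-up events go to the last treatment received. No sentence separates Week 6 from Week 7 for AEs.

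On timing, Protocol 5.1 tells families to "apply study patches to the hip once daily in the morning at approximately 8:00 am" and to remove the patch after 9 hours. Double-blind dosing begins on Day 36 and the crossover takes effect in Week 7, with no washout at either point. An open-label d-ATS patch is applied in clinic on Day 35 (Protocol 5.3.4.2).

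**The concern.** Treatment changes when a patch goes on in the morning, whereas the period changes at midnight. An AE that starts at 01:00 on Day 36 comes after a d-ATS patch and before any double-blind patch. The written rule still counts it as double-blind, and for a placebo-first child that is the placebo week.

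Every placebo week follows a d-ATS day: Day 35 in the placebo-first sequence and Day 42 in the d-ATS-first sequence. If AE rates are higher after d-ATS, a midnight cut moves some d-ATS-related onsets into the placebo column. The double-blind tables are the only AE summaries with a placebo column, and safety is a primary objective, so the dilution would run toward hiding harm.

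The period and the dose at onset can also disagree. At 01:00 on Day 36 no double-blind dose has been taken, and the SAP does not say which of the two prevails.

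**Working it through.** The documents give no figure for this, so there is nothing to reproduce. AE rates are not given either; those below are assumptions.

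**Inputs from the documents.** Application at about 08:00 and 9 hours of wear (Protocol 5.1). First double-blind patch on Day 36, last Week 6 patch on Day 42, first Week 7 patch on Day 43. Two sequences at 1:1 (SAP 3.2). About 90 randomised, so about 45 per sequence.

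**Clock arithmetic.** A patch applied at 08:00 comes off at 17:00. The gap to the next patch is 7 + 8 = 15 hours. The 7 hours before midnight keep the correct date. The 8 hours from 00:00 to 08:00 carry the next date. Share of a treatment week: 8/168 = 4.8%.

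**Effect on the rate ratio.** Assume a constant hazard of 1 on placebo and R on d-ATS, with the hours up to the next patch belonging to the previous patch.

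*Date cut at both boundaries (Day 43 is hypothetical):*
- Placebo week, both sequences: (160 + 8R)/168.
- d-ATS week: R in the d-ATS-first sequence and (160R + 8)/168 in the placebo-first sequence, where the preceding night is a placebo night.
- At R = 2: placebo 176/168 = 1.048; d-ATS (2 + 328/168)/2 = 1.976; ratio 1.976/1.048 = 1.89.

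*Date cut at Day 36 only (the written rule), with Day 43 cut at the patch:*
- Week 6 then runs 176 hours. Placebo-first: placebo 168 + 8R, d-ATS 168R. d-ATS-first: d-ATS 176R, placebo 168.
- Averages: placebo 168 + 4R, d-ATS 172R.
- At R = 2: 344/176 = 1.95.

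| True ratio R | Placebo inflation, both cuts | Observed ratio, both cuts | Observed ratio, Day 36 only |
|---|---|---|---|
| 1 | 0% | 1.00 | 1.00 |
| 1.5 | 2.4% | 1.45 | 1.48 |
| 2 | 4.8% | 1.89 | 1.95 |
| 3 | 9.5% | 2.70 | 2.87 |

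**Sensitivity to overnight onset.** At R = 2 with both cuts, placebo inflation is 1.2%, 2.4%, 4.8% or 9.5% if the overnight hazard is 0.25, 0.5, 1 or 2 times the even-spread value.

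**Events moved.** With d-ATS rates of 0.2, 0.5 or 1.0 AE per subject-week, the d-ATS-rate events that enter the placebo column number 45 × rate × 8/168 = 0.4, 1.1 or 2.1 at Day 36. With both boundaries (90 × rate × 8/168) they number 0.9, 2.1 or 4.3.

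**One event type.** Assume new sleep-related events at 10% per week on d-ATS and 2% on placebo, spread evenly over seven nights, with a fraction f = 0.5 starting after midnight and date cuts at both boundaries. Follow-up events stay with the last treatment.
- Placebo: d-ATS-first 2% + 10% × 0.5/7 = 2.71%; placebo-first 2% + (10% − 2%) × 0.5/7 = 2.57%; average 2.64%.
- d-ATS: d-ATS-first 10%; placebo-first 10% + 2% × 0.5/7 = 10.14%; average 10.07%.
- The difference is 7.43 points instead of 8.0, a shrinkage of 7% (4% to 11% for f from 0.25 to 0.75). The placebo shift of 0.64 points is about 0.6 of 90 children.

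**The case against.** A reader might infer more than the documents support, in four ways.

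- *That the SAP misassigns events at the crossover.* It does not say so. The date rule covers only the open-label/double-blind boundary. For Day 42/43, SAP 7.7.1 refers to the dose at onset, and its follow-up rule uses the last treatment received; both could lead to the correct assignment. The fallback for an incomplete start date hints at a date-based derivation without stating one. The finding there is an unspecified cut.
- *That the same-date sentence in SAP 5 assigns treatment.* It decides whether an event is treatment-emergent at the first patch. It does not decide which treatment is charged on Day 36 or Day 43.
- *That sleep problems start in the affected hours.* Protocol 6.19 lists "headache, decreased appetite, stomach ache, trouble sleeping, nervousness, mood swings" among anticipated events but gives no timing. Trouble falling asleep that begins before midnight keeps the correct date. Trouble already present from up to five weeks of open-label d-ATS is not a new onset unless it worsens, so spreading onsets evenly over the week probably overstates the shift.
- *That placebo-week harms are inflated and the primary safety result is biased.* Inflation needs a higher AE rate after d-ATS, and no rates are given. The safety objective names no comparison with placebo. SAP 7.7 plans no inferential statistics, and all data are listed.

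These points limit the claim and its size. The written Day 36 rule remains: it ignores a recorded time and puts some d-ATS-related onsets in the double-blind period. The Week 6/Week 7 gap also remains, because a table by treatment arm cannot be programmed without some cut.

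**Conclusion.** The point holds as a minor one. At Day 36 the stated rule places onsets between midnight and the first patch in the wrong period. At Day 43 the rule is missing, and the same misplacement follows only if the date logic is carried over.

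The consequence is conditional: a modest dilution of the descriptive d-ATS versus placebo AE comparison if AE rates are higher after d-ATS. A true rate ratio of 2 would appear as about 1.95 from the written rule alone, or about 1.89 with date cuts at both boundaries. These figures rest on a constant hazard, patches at 08:00 and assumed rates. The dilution is smaller if few onsets occur overnight and larger if they cluster there. No hypothesis test or decision rule is affected.

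**What to change.** In SAP 5 and 7.7.1, assign each TEAE by onset date and time relative to the first patch of each double-blind week:

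- onset before the first Day 36 patch goes to Dose-Optimization;
- onset before the first Week 7 patch goes to the Week 6 treatment;
- the date rule applies only when the onset time or the patch time is missing, and the number of events handled that way is reported.

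Derive the dose at onset from the same cut, so that period and dose agree. Settle the wording before unblinding.

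The cost is a few sentences and one derivation; onset time is already collected. There are two limits. Onset times may be parent-reported and imprecise. The documents also do not confirm that the dosing diary records the clock time of patch application; if it does not, the date rule would still apply to many events, and the reported count would show how many.
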